7 PROCEDURES

The procedures required at each visit are described below. The times indicated in the following sections and Appendices are based on the visit starting in the AM with each visit starting at a consistent timeframe relative to Visit 1.

7.1 Visit 1: Screening Day -14 (14 days prior to Visit 2)

Procedures will be completed at Visit 1 in the following general order. The visit will start between approximately 8:00AM and 11:00AM. All subjects who sign an informed consent document will be assigned a unique 6-digit screening number (i.e., XXX-XXX, which will be a compilation of the site number (first 3 digits) and subject number (last 3 digits). This subject number will be unique within this trial and will be used to identify the subject throughout the study.

- Obtain written informed consent
- Administer ocular symptom questionnaires (SANDE Part 1 only, SPEED, and a 7-item symptom questionnaire) before other procedures
- Review of the medical history
- Review concomitant medication history in the past 28 days
- Vital signs (pulse, blood pressure, temperature and respiration rate), height and weight
- BCVA
- Biomicroscopy and external eye examination
- Tear osmolarity
- TBUT
- Assessment of Meibomian glands
- Staining procedures conducted in the following order (refer to Manual of Procedures):
 - Corneal staining
 - o Bulbar conjunctival staining
 - Staining of the lid wiper area of the upper eyelid (with photographs taken if technology is available)
- Abbreviated physical exam (including eyes, ears, nose, throat (EENT), respiratory, cardiovascular, musculoskeletal, gastrointestinal, and dermatological)
- Collect blood for Hematology and Chemistry
- Urine pregnancy test (women of child-bearing potential only)
- Schirmer's test
- IOP)
- Review eligibility criteria
- Once all other procedures and assessments have been completed, review the qualification criteria and if the subject qualifies for the study, determine which eye is the Study Eye
- Instruct subject in study drug instillation technique and observe/correct technique using study drug dispensed at this visit.
- Complete drop instillation comfort questionnaire within 5 minutes after dosing for the Fellow Eye (the non-study eye)
- Assess adverse events during this visit

• At the end of the visit, the subject will be scheduled for Visit 2, 14 days from this visit, will receive their study medication to take home, and provided with the instructions in Section 7.1.1.

In the event that the subject does not qualify at Visit 1, the subject may be rescreened.

7.1.1 Subject Instructions

The following instructions will be provided to the subject before leaving the clinic.

- Store your study drug at room temperature and out of the reach of children. Only you should use your study drug.
- Instill your study medication into each eye three times daily. Study doses are to be taken approximately at the times of the meals. If you miss a dose, do not double-up or catch-up, but instead, resume taking your three times daily schedule as soon as possible.
- Open a pouch containing a single vial of study medication for every dose. Instill one drop of study medication from this newly opened vial into each eye, starting with the mid-day dose on the day of your clinic visit. Open a new pouch and vial for every dose.
- Continue to refrain from use of Aspirin with the exception of low dose aspirin (81mg) and NSAIDs such as ibuprofen (Advil®or Motrin®) or naproxen (Aleve®)
- Continue to refrain from use of contact lenses and any and all eye drops for dry eye or any other reason
- Continue to refrain from other disallowed medications
- Call the study clinic if you experience any problems, including more that your usual eye redness or discomfort
- On the morning of your next clinic visit, DO NOT TAKE your morning dose of study medication.
- Return to the clinic for your next appointment and remember to bring all used and unused study medication with you.

7.2 Phone Call: Day -7 (7 days ±1 day after Visit 1)

Site personnel will have an interim phone call to remind subjects to administer their medication and to assess if any adverse events have occurred since Visit 1. This phone call and attempts will be documented.

7.3 Visit 2: Randomization and Treatment Day 1

Procedures will be completed at Visit 2 in the following general order. This visit should take place between approximately 8:00AM and 11:00AM and at approximately the same time as Visit 1:. Subjects will be evaluated to determine if they are eligible for randomization to the double-masked treatment portion of the study.

- Administer symptom questionnaires (SANDE Part 1 and 2, SPEED, and 7-item symptom questionnaire) before other procedures and before dosing
- Collect previous study medication supplies from subject

- Document date and time of last dose of study medication
- Review concomitant medications and medical changes since last visit
- Assess adverse events since the last visit and during this visit
- Collect vital signs (pulse, blood pressure, temperature and respiration rate)
- BCVA
- Biomicroscopy and external eye examination
- Tear collection for biomarkers
- TBUT
- Staining procedures conducted in the following order (refer to Manual of Procedures):
 - o Corneal staining
 - o Bulbar conjunctival staining
 - o Staining of the lid wiper area of the upper eyelid (with photographs taken it technology is available)
- Impression cytology (with anesthesia, in Study Eye only)
- Confirm continued eligibility for participation per Randomization Criteria (Section 6.3)

Subjects who continue to qualify for the study will be randomly assigned to double-masked treatment (Section 8.4) and will be provided with an identically appearing kit of study medication corresponding to their assigned treatment. Subjects who fail to qualify for this study will be considered screen failures and will be withdrawn from the study with the reason for disqualification documented.

For continuing subjects, the following will be done:

- Once all other procedures and assessments have been completed, observe/correct subject's study drug instillation technique using new study drug dispensed at this visit.
- Complete drop instillation comfort questionnaire within 5 minutes after dosing for the Fellow Eye (the non-study eye)
- At the end of the visit, the subject will be scheduled for Visit 3 in 14 days from this visit, will receive their study medication to take home, and provided with the instructions provided in Section 7.1.1.

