6.3 Randomization Criteria

At the Visit 2 (Randomization and Treatment Day 1), an eligible subject must continue to meet the following Randomization Criteria:

- 1. Have no clinically important changes in medical status or changes in concomitant medications since Visit 1 that would affect study participation or confound the evaluation of safety or efficacy.
- 2. Have a score of >20 but less than 90 for both symptom frequency and symptom severity on the SANDE scale (Part 1) (Appendix IV)
- 3. Continue to meet the following dry eye entry staining criteria, in the Study Eye that qualified at Visit 1. If both eyes qualified at Visit 1, either eye could be eligible to continue to qualify for randomization:
 - a. Total corneal staining score $\ge 2/15$ and ≤ 10 on the National Eye Institute (NEI)/Industry scale with a ≥ 2 in at least one region
 - b. Total bulbar conjunctival staining score of $\geq 2/18$ and ≤ 10 on the NEI/Industry scale with a ≥ 2 in at least one region

6.4 **Definition of Study Eye**

For the purpose of efficacy analysis in this trial, each subject will have only one study eye. If a subject has only one qualifying eye, this eye will be the Study Eye. If both eyes of the subject qualify, then the Study Eye will be the eye with the highest total corneal staining score. If the scores for total corneal staining are the same, the Study Eye will be the right eye. The non-study eye is referred to as the "Fellow Eye".

If at Visit 2 the Study Eye does not qualify based on randomization criteria, but the subject had both eyes qualify at Visit 1 and the other eye continues to qualify based on randomization criteria, that eye will become the Study Eye.

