9.2 Assessment of Signs

9.2.1 Tear Collection for Biomarkers of Inflammation

Tear collection for biomarkers of inflammation will be assessed in both eyes at Visits 2, 3, and 4. Tear collection must be done under the slit lamp by the Investigator before any staining of the eye has occurred. Tears collected will be assessed for prostaglandins (from the Study Eye) and MMP-9 activity (from the Fellow Eye). Information on collection procedures, sample handling, labeling and storage is provided in the Study Manual.

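### Protocol 7.3 lists Visit 2 impression cytology before eligibility is confirmed and with no step to re-confirm the Study Eye, so some subjects may have an avoidable procedure or a cytology baseline from the other eye

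*Protocol*

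**What the plan says.** Protocol 7.3 introduces its list with "Procedures will be completed at Visit 2 in the following general order". After the questionnaires, medication review and safety checks come tear collection, TBUT, the three staining assessments, then "Impression cytology (with anesthesia, in Study Eye only"), and last "Confirm continued eligibility for participation per Randomization Criteria (Section 6.3"). The text after the list adds: "Subjects who fail to qualify for this study will be considered screen failures and will be withdrawn from the study".

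On the Study Eye, Protocol 6.4 (and 5.1) provides for a change under this condition: "If at Visit 2 the Study Eye does not qualify based on randomization criteria, but the subject had both eyes qualify at Visit 1". The second eye then takes over, provided it still meets the criteria. Protocol 11.1 fixes the Study Eye at randomization.

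On tears, Protocol 9.2.1 states: "Tear collection for biomarkers of inflammation will be assessed in both eyes at Visits 2, 3, and 4". It also requires: "Tear collection must be done under the slit lamp by the Investigator before any staining of the eye has occurred". The assays are split by eye: "Tears collected will be assessed for prostaglandins (from the Study Eye) and MMP-9 activity (from the Fellow Eye").

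Cytology is done in the Study Eye only, at Visits 2 and 4 (9.2.4). Its one timing rule is Appendix I footnote j, which places it after corneal, conjunctival and lid wiper staining.

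**The concern.** The staining scores settle whether the subject can be randomized and whether the Study Eye moves. In the listed order they are available before cytology, yet the check that uses them comes after it. Visit 1 (7.1) has an explicit step to determine the Study Eye before the one eye-specific task that follows, the drop comfort question. Visit 2, where the eye can change, has no such step.

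Two things are at stake. Subjects who will not be randomized may undergo an anesthetized sampling procedure for no analytic purpose. In a switched subject, change from baseline in gene expression may compare one eye at Visit 2 with the other at Visit 4. The SAP has no rule that would catch this: its Study Eye definitions (1.1 and 3.3.7) omit the Visit 2 switch, and its baseline rule (3.3.7) takes the last non-missing pre-dose value without requiring the same eye. In the biomarker ANCOVA (5.2.6), baseline enters both the change score and the covariate, so a cross-eye value would act twice.

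**Working it through.** The documents state no figure for this point, so the check compares sections and bounds the counts.

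**1. Could eligibility be judged before cytology?** Protocol 6.3 has three randomization criteria.
- Medical status and medication changes are reviewed early in the 7.3 list.
- SANDE Part 1 is completed before any other procedure (7.3, 9.1).
- Corneal and bulbar staining are listed before cytology.

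All three are therefore available. Footnote j sets only a lower limit on cytology timing (after staining). Nothing requires cytology to precede the eligibility check.

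**2. Is a failing subject's sample used?** Exploratory analyses are on the mITT population (11.4.4; SAP section 10). That population contains only randomized subjects (11.1; SAP 4.1), so the sample enters no planned biomarker analysis.

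**3. How many subjects could fail at Visit 2?** Protocol 5.1 gives about 125 screened and 65 randomized: 125 − 65 = 60 not randomized (60/125 = 48%). The split between Visit 1 and Visit 2 is not given, so the bound is 0 to 60. For illustration, with an assumed share of those failures falling at Visit 2:
- 25%: 0.25 × 60 = 15
- 50%: 0.50 × 60 = 30
- 75%: 0.75 × 60 = 45

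These are ceilings on unneeded cytology. A site that acts at once on a SANDE or medication failure would stop before sampling.

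**4. How many subjects could switch?** A switch needs both eyes to qualify at Visit 1, and at Visit 2 the first to fail and the other still to qualify. No rate is given. An assumed 2% to 20% of 65 gives 0.02 × 65 = 1.3 to 0.20 × 65 = 13, or about 1 to 13 subjects.

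**5. Which endpoints are exposed?** From SAP 5.2.5:
- Cytology: 6 genes × 2 sites = 12 changes, at risk if the old eye is sampled at Visit 2.
- Tears: 1 (MMP-9) + 5 (prostaglandins) = 6 changes, at risk only if the assay is fixed to an eye at collection.
- SANDE is one score per subject. Staining and TBUT are assessed in both eyes (9.2.2, 9.2.3), so the new Study Eye has its own baseline. None of these is exposed.

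**The case against.** The order is described as general, so a site may confirm eligibility after staining and before cytology without departing from the protocol. A site that applies 6.4 as soon as staining is read would sample the new Study Eye even in the listed order, because the last step confirms eligibility and does not say that the switch waits for it. Figure 2 (sequence of ocular assessments) is not visible in the text available, and the Study Manual, which governs sample handling and labelling, was not supplied; either may already deal with part of this. Any switch precedes randomization, so a cross-eye baseline should add noise rather than bias between arms.

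All of this stands. It makes the problem a risk rather than a certainty, but leaves its avoidance to each of about 7 sites when reordering the list would remove it.

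A reader might infer that every switched subject has all 18 biomarker baselines from the wrong eye. The documents do not support that. Tears are taken from both eyes and no section ties an assay to an eye at collection, so the assays could be assigned once the Study Eye is final. A reader might also count tear collection before staining as part of the fault. It is an explicit requirement of 9.2.1 and Appendix I footnote h, and should stay.

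**Conclusion.** The point holds as a low-cost clarification. In the listed order, cytology precedes the eligibility check and no step re-confirms the Study Eye, although everything needed for both is already known. The possible consequences are an avoidable procedure in subjects who fail at Visit 2 and a cross-eye comparison in up to 12 exploratory gene-expression changes per switched subject. The documents bound the failures only at 0 to 60 and do not give the switch rate; the illustrative counts rest on assumed shares. The 6 tear changes are an open question.

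It would be wrong to conclude that run-in failures necessarily have unneeded cytology, or that the trial's main results are threatened. The order is not binding, and the primary endpoint, staining and TBUT are unaffected.

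**What to change.** - **Protocol 7.3:** move the eligibility confirmation to directly after staining and before impression cytology, and add confirmation of the final Study Eye at the same step.
- **Tears:** keep collection before staining and identify each sample as OD or OS. If the two samples are interchangeable, assign the prostaglandin and MMP-9 assays once the Study Eye is final. If they are not, exclude cross-eye changes from the biomarker analysis.
- **SAP 1.1 and 3.3.7:** add the Visit 2 switch rule to the Study Eye definition, and require that eye-specific baseline and follow-up values come from the same eye.

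The cost is a few lines in each document, with conforming wording in the Study Manual if needed. No visit, sample or test is added. If the tear samples are not interchangeable, tear data from switched subjects are lost to the change analyses. The alternative of leaving each assay in the eye first sampled would avoid that loss but would contradict 9.2.1, 11.4.4 and footnote h, and would leave prostaglandins measured in an eye that failed the criteria.

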7.4 Phone Call: Treatment Day 8 ±1 day

Site personnel will have an interim phone call to remind subjects to administer their medication and to assess if any adverse events have occurred since Visit 2. This phone call and attempts to contact the subject will be documented.

7.5 Visit 3: Treatment Day 15

Study procedures will be completed at Visit 3 in the following general order. The visit should take place between approximately 8:00AM and 11:00AM and at approximately the same time as Visit 1:

- Administer symptom questionnaires (SANDE Part 1 and 2, SPEED, and a 7-item symptom questionnaire) before other procedures and before dosing
- Collect previous study medication supplies from subject

- Document date and time of last dose of study medication
- Review concomitant medications and medical changes since last visit
- Assess adverse events since the last visit and during this visit
- Collect vital signs (pulse, blood pressure, temperature and respiration rate)
- Biomicroscopy and external eye examination
- Tear collection for biomarkers
- TBUT
- Staining procedures conducted in the following order (refer to Manual of Procedures):
 - Corneal staining
 - o Bulbar conjunctival staining
 - Staining of the lid wiper area of the upper eyelid (with photographs if technology is available)
- Collect blood for serum potassium
- Once all other procedures and assessments have been completed, observe/correct subject's study drug instillation technique using study drug dispensed at this visit.
- Complete drop instillation comfort questionnaire within 5 minutes after dosing for the Fellow Eye (the non-study eye)
- At the end of the visit, the subject will be scheduled for Visit 4 in 14 days from this visit, will receive their study medication to take home, and provided with the instructions provided in Section 7.1.1.

7.6 Phone Call: Treatment Day 22 ±1 day

Site personnel will have an interim phone call to remind subjects to administer their medication and to assess if any adverse events have occurred since Visit 3. This phone call and attempts will be documented.

7.7 Visit 4: Day 29

Procedures will be completed at Visit 4 in the following general order. The visit should take place between approximately 8:00AM and 11:00AM and at approximately the same time as Visit 1:

- Administer symptom questionnaires (SANDE Part 1 and 2, SPEED, and a 7-item symptom questionnaire) before other procedures and before dosing
- Collect previous study medication supplies from subject
- Document date and time of last dose of study medication
- Review of concomitant medications and medical changes since last visit
- Assess adverse events since the last visit and during this visit
- Collect vital signs (pulse, blood pressure, temperature and respiration rate) and weight
- BCVA
- Biomicroscopy and external eye examination
- Tear collection for biomarkers
- TBUT
- Staining procedures onducted in the following order (refer to Manual of Procedures):
 - Corneal staining
 - o Bulbar conjunctival staining

- Staining of the lid wiper area of the upper eyelid (with photographs if technology is available)
- Impression cytology (with anesthesia, in Study Eye only)
- Abbreviated physical exam (including EENT, respiratory, cardiovascular, musculoskeletal, gastrointestinal, and dermatological)
- Collect blood for Hematology and Chemistry
- Urine pregnancy test (women of child-bearing potential only)

Once all the following assessments are complete, the subject will be discharged from the treatment portion of the study. Investigators will counsel the subject on the appropriate treatment regimen. The subjects will be reminded that they will receive a call from the site 5-9 days after this visit to follow up with them.

7.8 Follow up telephone call (7± 2days after Visit 4)

A follow-up telephone call will be conducted 7 ± 2 days after Visit 4 and the following will be assessed:

- Review of concomitant medications and medical changes since last visit
- Assess adverse events since the last visit

7.9 Early Termination Visit

The purpose of the Early Termination visit is to obtain critical information about the subject's participation, and should be scheduled preferably before there has been a substantial lapse in study medication usage. However, even if there has been a medication lapse, the subject should be encouraged to return to the clinic for this visit, and should be instructed to return all study medication. The following assessments will be performed at the Early Termination Visit for randomized subjects who are withdrawn from the study prematurely:

- Collect previous study medication supplies from subject
- Document reason for early termination
- Document date and time of last dose of study medication
- Assess adverse events since the last visit and during this visit
- Assess concomitant medications and medical changes since last visit
- Collect vital signs (pulse, blood pressure, temperature and respiration rate), and weight
- Abbreviated physical exam (including EENT, respiratory, cardiovascular, musculoskeletal, gastrointestinal, and dermatological)
- Biomicroscopy and external eye examination
- Collect blood for Hematology and Chemistry
- Urine pregnancy test (women of child-bearing potential only)

Once these assessments have been complete, the subject may be discharged from the study, provided that there is no need for additional follow-up to continue to monitor an adverse event or other condition.

7.10 Unscheduled Visit

Though not anticipated, subjects may need to be seen at other times than the scheduled study visits for additional safety assessments or to follow-up, as medically necessary, on adverse event or other findings. If an additional study visit occurs, the date and nature of the visit will be documented in the CRF and in the source documents.

7.11 Potential Toxicity Management

There is no systemic toxicity expected in this study. All preclinical evidence indicates that systemic exposure of P-321 via ocular topical administration is minimal at doses up to 4-fold higher than the daily dose planned in this study (the estimated systemic safety margins for the maximal dose anticipated in this study is 75-fold). However, since P-321 is an ENaC inhibitor, a previous potential safety signal of concern following the administration of P-321, was druginduced hyperkalemia. This possibility was carefully investigated in Study P-321-101, a clinical trial evaluating multiple concentrations including 0.01%) P-321 Opthalmic solution taken BID for 28 days. In that study, pharmacokinetic results demonstrated a lack of systemic availability of 0.01% P-321 Ophthalmic Solution. No changes in plasma or serum potassium were noted in subjects administered 0.01% P-321 Ophthalmic Solution BID for up to 28 days. We will monitor serum potassium levels in this study.

Additional information is provided in the Investigator's Brochure.

8 TREATMENT OF SUBJECTS

8.1 Description of Study Drug

P-321 Ophthalmic Solution 0.017% is a sterile, aqueous, non-preserved solution with pH of approximately 5, and tonicity of approximately 290 mOsm/kg. Placebo solution has identical composition without the active ingredient. Both solutions are packaged in low density, polyethylene dropper bottles. Each bottle is intended for a single administration on each eye.

Table 1 P-321 Ophthalmic Solution: 0.017% Investigational Product

	Investigation	onal Product			
Product Name:	P-321 Ophthalmic Solution 0.017%	Matching placebo (vehicle with no active ingredient)			
Dosage Form:	Sterile unpreserved ophthalmic solution for ocular instillation	1 1 1			
Unit Dose	Vial intended for a single-dose	Vial intended for a single-dose			
Route of Administration	tration 1 drop in each eye three times daily 1 drop in each eye daily				
Physical Description	Aqueous solution, pH 5, approximately 290 mOsm/Kg	Aqueous solution, pH 5, approximately 290 mOsm/Kg			
Manufacturer	Bio-Concept Laboratories, Inc.	Bio-Concept Laboratories, Inc.			

